2.1.2.2 Part B

The primary endpoints for Part B of the trial are the MTD of BI 891065 in combination with BI 754091 and the number of patients with DLTs during the first treatment cycle. Q.D. and b.i.d. dosing schedules may be explored in Part B. The MTD is defined as the highest dose combination with less than 25% risk of the true DLT rate being equal to or above 33%.

The primary endpoints of this part will be evaluated based on a timeframe from first treatment administration until the end of the MTD evaluation period (the end of the first cycle).

Another BLRM employing the EWOC principle will be used during the escalation phase for selection of dose combinations and for estimation of the MTD. It is planned that cohorts of patients will receive escalating doses of BI 891065 in combination with BI 754091 (at the dose pre-specified by the SRC) until the MTD is reached or the highest tolerated dose of BI 891065 determined in Part A has been tested. Each cohort will consist of newly enrolled patients. Estimation of the MTD during the combination escalation phase of the trial will be based upon the estimation of the probability of a DLT in Cycle 1 in the set of evaluable

patients for MTD. The corresponding methodology is described in Section 7 and in the statistical appendix (see Appendix 10.5). The MTD estimate established during the dose escalation of Part B will be re-investigated at the end of Part B by re-running the BLRM using the DLT information from all treatment cycles to determine the recommended dose combination for further development.

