In both Parts A and B, the SRC will recommend and decide on the size for the next dose escalation cohort. After all patients in a cohort in Part A and Part B have either experienced a

DLT or have been observed for at least the MTD evaluation period without experiencing a DLT, the BLRM will be updated with the newly accumulated data. The overdose risk will then be calculated for each dose, and escalation will be permitted to all doses (dose combinations in Part B) which fulfil the EWOC criterion and the additional maximum 100% escalation rule. Based on the model and on additional information (e.g., PK, PDc, patient profiles, cumulative safety outputs), the members of the SRC will reach a joint decision on the next dose level to be investigated.

For dose levels above 15 mg, if DLTs are observed in the first two consecutive patients of a previously untested dose level, subsequent enrolment to that cohort will be stopped. The BLRM will be re-run to confirm that the dose level still fulfils the EWOC principle. Based on this information, the SRC will evaluate whether the next patients will be enrolled at the same dose level, or if they will be enrolled at a lower dose level.

The SRC may recommend stopping the dose-finding phase after the criterion for MTD (see Section 7) is fulfilled. Further patients may be included to confirm this MTD estimate (i.e., to confirm that the EWOC criterion is still fulfilled). If no DLT is observed at a dose of which the efficacy is considered sufficient, the SRC may decide to include an additional number of patients at the same dose level and to declare this dose as the recommended dose for further development. The SRC can declare any dose fulfilling the EWOC criterion as recommended dose for further development, independent of the MTD estimate.

Once the combination dose is determined (to be confirmed by the Sponsor), the Part C expansion cohort will be initiated in patients with NSCLC who failed an anti-PD-1/anti-PD-L1 treatment as a first-line therapy, either by itself or in combination with platinum-based therapy (see Section 3.3.2). In Part C, the SRC will assess the safety data and trial conduct in regular intervals as described in the SRC documentation. In addition, Part C will further evaluate the efficacy of the combined compounds. The trial design is displayed in [Figure 3.1: 1](#).

Patients in Parts B and C may receive either q.d. or b.i.d. BI 891065

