$a_{1,k}, a_{2,k}$ the prior mixture weights ($a_{1,k} + a_{2,k} = 1$), $k = 1, 2$ and

$f_i(\theta_k) = \text{MVN}(\mu_{ik}, \Sigma_{ik})$ a bivariate normal distribution with mean vector μ_{ik} and covariance matrix Σ_{ik} where

$$\Sigma_{ik} = \begin{pmatrix} \sigma_{ik,11}^2 & \sigma_{ik,11}\sigma_{ik,22}\rho_{ik} \\ \sigma_{ik,11}\sigma_{ik,22}\rho_{ik} & \sigma_{ik,22}^2 \end{pmatrix}$$

Mixture prior distributions have the advantage that they allow for specification of different logistic dose-toxicity curves, therefore making the prior more robust.

The priors for θ_k ($k=1, 2$) will be derived using the meta-analytic predictive approach. They will take into account available data from Part A of this trial and available data from the monotherapy dose escalation part of BI trial 1379.6 for the prior of BI 891065 and available data from the BI trial 1381.1 that aims to determine the MTD of BI 754091.

A weakly informative normal prior distribution will be used for η .

The derivation of these prior distributions is described in Appendix 10.5.

The estimated probability of DLT π_{12,d_1,d_2} at each dose combination d_1, d_2 from the model will be summarised using the following intervals:

Under dosing: [0.00, 0.16)

Targeted toxicity: [0.16, 0.33)

Over dosing: [0.33, 1.00]

The BLRM recommended dose combination for the next cohort is the combination with the highest posterior probability of the DLT rate falling in the target interval [0.16, 0.33) among the dose combinations fulfilling the EWOC principle. Per EWOC it should be unlikely (<25% posterior probability) that the DLT rate at the dose combination will be ≥ 0.33 .

However, the maximum allowable dose increment for the subsequent cohort will be no more than 100 % for each drug.

The MTD may be considered reached if one of the following criteria is fulfilled:

- The posterior probability of the true DLT rate in the target interval [0.16 – 0.33] of the MTD is above 0.50, or
- At least 12 patients have been treated in the trial, of which at least 6 at the MTD.

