Scenarios 4 and 5 illustrate that when 3 patients have been treated at 100 / 240 without DLT and then additional 3 patients have been treated at 200 / 240 without DLT, the model would still recommend to treat the next patient with 200 / 240. Only in the case 4 or more patients are treated with 200 / 240 without experiencing a DLT, the model recommends to escalate to 400 / 240. Scenarios 9 and 10 show that in case one patient experiences a DLT at 200 / 240, the model requires 9 additional patients without DLT to allow escalating to 400 / 240.

Scenarios 11 and 12 illustrate possible ways to declare 400 / 240 as the MTD.

Table 10.5: 11 Hypothetical data scenarios

Scenario	Dose [combination] (mg)	# Patients	# DLT	Current Dose [combination]: P (OD)	Next recommended dose [combination]	Next dose [combination]:		
						P (UD)	P (TD)	P (OD)
1	100 / 240	3	0	0.012	200 / 240	0.548	0.369	0.083
2	100 / 240	3	1	0.066	200 / 240	0.335	0.453	0.212
3	100 / 240	3	2	0.256	50 / 240	0.444	0.381	0.175
4	100 / 240	3	0	0.027	200 / 240	0.691	0.282	0.027
	200 / 240	3	0					
5	100 / 240	3	0	0.021	400 / 240	0.488	0.277	0.234
	200 / 240	4	0					
6	100 / 240	3	0	0.117	200 / 240	0.420	0.463	0.117
	200 / 240	3	1					
7	100 / 240	3	0	0.308	100 / 240	0.534	0.412	0.054
	200 / 240	3	2					
8	100 / 240	3	0	0.048	200 / 240	0.547	0.405	0.048
	200 / 240	6	1					
9	100 / 240	3	0	0.014	400 / 240	0.434	0.318	0.249
	200 / 240	10	1					
10	100 / 240	3	0	0.017	400 / 240	0.819	0.164	0.017
	200 / 240	4	0					
	400 / 240	6	0					
11	100 / 240	3	0	0.101	400 / 240	0.522	0.377	0.101
	200 / 240	4	0					
	400 / 240	6	1					
12	100 / 240	3	0	0.107	400 / 240	0.488	0.405	0.107
	200 / 240	10	1					
	400 / 240	6	1					

Operating characteristics

Operating characteristics are a way to assess the long-run behaviour of a model by illustrating the precision of the design in estimating the MTD. Under an assumed true dose-toxicity curve, metrics such as the probability of recommending a dose combination with true DLT rate in the target interval can be approximated via simulation. [Table 10.5: 12](#) describes 4 assumed

true dose-toxicity scenarios that were used to assess the operating characteristics of the model. These scenarios reflect a wide range of possible cases as follows:

- Scenario 1: aligned with prior means
- Scenario 2: high-toxicity scenario
- Scenario 3: low-toxicity scenario
- Scenario 4: non-logistic dose-toxicity scenario

Table 10.5: 12 Assumed true dose-toxicity scenarios

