Scenario		Dose combination (mg/mg)			
		50 / 240	100 / 240	200 / 240	400 / 240
1: Prior	P(DLT)	0.118	0.147	0.211	0.342
2: High Tox		0.156	0.298	0.379	0.514
3: Low Tox		0.051	0.092	0.137	0.254
4: Non-Logistic		0.098	0.112	0.317	0.675

For each of these scenarios, 1000 trials were simulated. Each cohort consisted of 3 patients and dose escalation complied with the following rules:

1. Escalate to the dose combination which maximises the probability of the targeted toxicity region and satisfies the overdose criterion if it is $\leq 100\%$ increase from the current dose of BI 891065
2. If the recommended dose combination satisfying the overdose criterion is $> 100\%$ increase in dose of BI 891065, then escalate to the highest dose combination which is $\leq 100\%$ increase from the current dose of BI 891065.

The MTD was considered reached if at least 6 patients have been evaluated at a dose level which is the model's recommendation for the next dose cohort and if in total at least 12 patients have been included in the trial or if the posterior probability of targeted toxicity was at least 50% for the dose combination which is the model's recommendation for the next dose cohort and if in total at least 12 patients have been included in the trial.

It was then assessed how often a dose combination was declared as MTD with true DLT rate in the under-dose, targeted dose, or over-dose range. Furthermore, the average, minimum and maximum number of patients per trial and the average number of DLTs per trial are reported. Results are shown in [Table 10.5: 13](#).

Table 10.5: 13 Simulated operating characteristics

	% of trials declaring a MTD with true DLT rate in				# Patients	# DLTs
	Underdose	Target dose	Overdose	Stopped	Mean (Min-Max)	Mean (Min-Max)
1	19.4	70.4	9.3	0.9	12.711 (3 - 30)	2.601 (1 - 8)
2	6.9	51.1	35.5	6.5	11.538 (3 - 30)	3.648 (1 - 12)
3	76.2	23.1	0.0	0.7	13.752 (6 - 30)	2.048 (0 - 7)
4	34.5	64.9	0.2	0.4	12.414 (6 - 27)	3.007 (1 - 9)

In Scenario 1, which reflects the case that the true dose-toxicity is aligned with prior means, 70.4% of the simulated trials declared the combination 200 / 240 mg as MTD. Only 9.3% of the simulated trials declared the dose combination 400 / 240 mg as MTD, which has an assumed true toxicity probability in the overdose interval.

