In Scenario 2 (high-toxicity scenario), more than 50% of simulated trials declared a dose as MTD with assumed true toxicity probability in the target interval. 35.2% of simulated trials declared 200 / 240 as MTD which has a true toxicity probability of 0.379 which is close to boundary between target dose interval and overdose interval. The high-toxicity scenario has the biggest number of stopped trials (6.5%). This is expected for such a scenario.

In Scenario 3 (low-toxicity scenario) the MTD was more often chosen as a dose combination with true toxicity probability in under-dose interval than in the target dose interval. In the majority of simulated trials (70.4%) the MTD was chosen as 200 / 240, which has an assumed true toxicity probability of 0.137 which is close to the boundary of the target dose interval.

[figure not shown]
Scenario 4 (non-logistic scenario) illustrates that even if the model assumption of a logistic dose-toxicity relationship is not fulfilled, the model still selects doses with true toxicity probability in the target interval as MTD in almost 65% of simulated trials. This illustrates that the model is not sensitive to model misspecification.

[figure not shown]
The mean patient numbers range from 11.5 patients (Scenario 2) to 13.8 patients (Scenario 3) and the maximum number of patients was 30. Therefore, the patient numbers are as expected and increase when moving away from the high-toxicity scenario.

[figure not shown]
By reviewing the metrics presented in [Table 10.5: 13](#), it can be seen that the model is not sensitive to different scenarios of truth. In general, this model is conservative due to the overdose control criteria. In all scenarios, the probabilities of recommending a dose combination with true $P(DLT) \geq 33\%$ as MTD are much smaller than probabilities of recommending a dose combination with true $P(DLT)$ between 16% and 33% as MTD.

[figure not shown]
On-study recommendations based on the model are consistent with the clinical decision making process, and should be considered in conjunction with other available clinical information by the BI clinical trial team and trial investigators in deciding the dose levels to be tested in order to determine the MTD estimate.

R version 3.5.1 and JAGS version 4.3.0 were used for data scenarios and simulations for Part B.

[figure not shown]
[figure not shown]
[figure not shown]

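### The Part B MTD rule in Protocol Section 7.1.2 has no patient minimum on its first criterion, but the rule simulated for Table 10.5: 13 required 12 patients on both criteria

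*Protocol*

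**What the plan says.** Section 7.1.2 of the Protocol lists two alternative criteria for the Part B MTD, and meeting one is enough:

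- Criterion 1: "The posterior probability of the true DLT rate in the target interval [0.16 – 0.33] of the MTD is above 0.50, or"
- Criterion 2: "At least 12 patients have been treated in the trial, of which at least 6 at the MTD"

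Appendix 10.5 (Part B, operating characteristics) describes the simulated rule. One branch needs at least 6 patients at the recommended dose, the other a target-interval probability of at least 50%. Each branch then adds the same condition: "recommendation for the next dose cohort and if in total at least 12 patients have been included in the trial".

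Section 2.1.2.2 treats the two places as one methodology for the set of evaluable "patients for MTD. The corresponding methodology is described in Section 7 and in the statistical appendix (see Appendix 10.5"). SAP Section 7.4 refers back to Protocol Section 7 for the model and adds no minimum.

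Appendix 10.5 concludes from Table 10.5: 13 that "it can be seen that the model is not sensitive to different scenarios of truth". It also says that, in every scenario, the probabilities of recommending a combination with a true DLT rate of 33% or more "as MTD are much smaller than probabilities of recommending a dose combination with true" rates between 16% and 33%.

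**The concern.** Operating characteristics belong to a specific decision rule. Table 10.5: 13 is the only visible evidence of how the Part B rule performs, and the MTD is a Part B primary endpoint. If the stated rule can declare an MTD at 6 or 9 patients while the simulated one cannot do so before 12, the table cannot be cited in support of Section 7.1.2.

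No worked example fills the gap. The highest target probability in Table 10.5: 11 is 0.463, so criterion 1 is never met there. The appendix states that "Scenarios 11 and 12 illustrate possible ways to declare 400 / 240 as the MTD", but those rows have target probabilities of 0.377 and 0.405 with 13 and 19 patients, so they rest on criterion 2.

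Criterion 2 also counts patients in the trial as a whole. Part A alone has 2 + 1 + 3 + 4 + 3 + 3 + 6 = 22 evaluable patients (Table 7.1.2: 2), so read literally its total of 12 is met before Part B starts.

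**Working it through.** **1. The published table is consistent with a 12-patient minimum.** If every declared trial has at least 12 patients and every stopped trial has at least the published minimum N, then mean N ≥ (share declared × 12) + (share stopped × minimum N). From Table 10.5: 13:

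| Scenario | Lower bound | Published mean N |
|---|---|---|
| 1 | 0.991 × 12 + 0.009 × 3 = 11.92 | 12.711 |
| 2 | 0.935 × 12 + 0.065 × 3 = 11.42 | 11.538 |
| 3 | 0.993 × 12 + 0.007 × 6 = 11.96 | 13.752 |
| 4 | 0.996 × 12 + 0.004 × 6 = 11.98 | 12.414 |

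**2. Model and inputs.** The five-parameter model of Section 7.1.2; the Table 10.5: 8 prior; true rates from Table 10.5: 12; start at 100/240; cohorts of 3; overdose probability below 0.25; escalation of at most 100%. Posteriors come from importance-weighted prior draws.

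**3. Reproducing the appendix.** With the BI 754091 reference dose of 3200 mg stated in Section 7.1.2, Table 10.5: 10 is missed by up to 0.167 and Table 10.5: 11 by up to 0.222. With an assumed 240 mg they reproduce to within 0.005 and 0.015. Results below therefore use 235 to 250 mg unless stated. Under the simulated rule at 240 mg, 5,000 trials per scenario give mean N of 12.6 / 11.8 / 13.2 / 12.2, close to the published values. Target-selection percentages agree less well: 70.8 / 56.8 / 20.2 / 57.9 against 70.4 / 51.1 / 23.1 / 64.9.

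**4. Criterion 1 can be met early.**

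- 0/3 DLTs at 100/240, then 2/6 at 200/240: P(target) 0.55 and P(overdose) 0.14 to 0.15 at 200/240, so it is met at 9 patients.
- 1/3 at 100/240, then 1/3 at 200/240, with the stated 3200 mg: P(target) 0.52 and P(overdose) 0.107, so it is met at 6 patients.

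The simulated rule allows declaration in neither case.

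**5. The rule as written against the simulated rule.**

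| | Scen. 1 | Scen. 2 | Scen. 3 | Scen. 4 |
|---|---|---|---|---|
| Declaration permitted before 12 patients, Section 7.1.2 | 45–46% | 70–71% | 27% | 58–59% |
| Same, only the dose just treated may be declared | 31–39% | 49–56% | 18–23% | 37–45% |
| Same, simulated rule | 0% | 0% | 0% | 0% |
| Mean N, Section 7.1.2 (240 mg) | 10.7 | 8.6 | 12.2 | 9.8 |

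Rows 1 and 2 enumerate all cohort-of-3 outcome paths. The 5,000-trial simulation at 240 mg gives 44 / 72 / 26 / 59%, and at an assumed 200 mg 46 / 79 / 24 / 57%.

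**6. Scenario 2, share of trials declaring a dose in the overdose range.**

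| Reference dose | 12-patient minimum | First permitted look | One confirming cohort of 3 |
|---|---|---|---|
| 235 mg | 30.2% | 36.2% | 29.8% |
| 240 mg | 28.8% | 48.9% | 30.8% |
| 245 or 250 mg | 33.5% | 52.1% | 34.2% |

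The gap is 6 to 20 points at the first permitted look and −0.4 to +2.0 points after one confirming cohort. At 200 mg the first-look change is only from 25.6% to 28.0%. The result is sensitive because the state 1/3 then 1/3 has an overdose probability of about 0.25, on the limit itself. At the first permitted look, target selection is higher without the minimum in Scenario 1 (73–81% against 70–74%) and Scenario 4 (71–80% against 57–67%), and equal in Scenario 3 (19%).

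**7. The appendix's conclusions against Table 10.5: 13.** Overdose against target selection is 9.3% v 70.4%, 35.5% v 51.1%, 0.0% v 23.1% and 0.2% v 64.9%. The claim that overdose selection is much smaller fails in Scenario 2. Target selection ranges from 23.1% to 70.4%, which is not insensitivity to the true curve.

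**8. Part A.** Section 7.1.1 and the Part A simulation differ similarly, but overdose selection is 7.1% (simulated) against 7.3% (stated) in Scenario 2 and 10.5% against 10.4% in Scenario 4.

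**The case against.** The wording in Section 7.1.2 is permissive, the SRC must agree, and Section 3.1 provides that "Further patients may be included to confirm this MTD estimate (i.e., to confirm that the EWOC criterion is still fulfilled"). A simulation has to turn such a rule into a fixed one, and the appendix says openly what it assumed. Section 3.1 also requires at least 3 patients per combination cohort (2 if both are evaluable and free of DLTs). Part B already had 6 + 8 + 5 = 19 evaluable patients (Table 7.1.2: 5), and the highest target probability in Table 7.1.2: 6 is 0.313. A 12-patient minimum therefore no longer binds, and nothing suggests an early declaration. The overdose figures depend on an assumed reference dose and on SRC behaviour.

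The simulated prior also assumed one DLT in six at 400 mg in Part A, where none was seen. SAP Section 7.4 places the Part B prior in its Section 9.1, which is not in the public text and might contain more.

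All of this limits the consequence, and the overdose effect should be quoted only as a range. It does not remove the mismatch: the difference between the rules is unexplained, and no visible text attaches the minimum to criterion 1. The appendix's commentary does report some unfavourable Scenario 2 and 3 figures, which makes its summary sentences harder to defend.

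**Conclusion.** The concern holds. That Table 10.5: 13 describes a rule other than the one in Section 7.1.2 follows from the text alone and needs no simulation. The frequent permission to declare before 12 patients (roughly a quarter to seven-tenths of trials) is stable across assumed reference doses of 200 to 250 mg. The Scenario 2 overdose effect is not: about 0 to 20 points, and near zero if one confirming cohort is added. Some published cells are reproduced only to within about 8 points, so the comparison between rules is informative and the absolute levels are not. The two summary conclusions are wrong on the table's own figures. The Part A discrepancy is negligible. This should be fixed as an error in a stated design property; it does not alter remaining Part B decisions.

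**What to change.** Reconcile Section 7.1.2 and Appendix 10.5 in one of two ways:

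- **(a)** Add to criterion 1 that at least 12 patients have been treated in Part B, and make criterion 2 refer to Part B instead of the trial. This is wording only, with no extra patients.
- **(b)** Simulate the rule exactly as Section 7.1.2 states it and replace Table 10.5: 13. This costs one rerun of the existing code; the prior and BI 754091 reference dose used should be stated with the results.

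Under either option, settle whether the target probability must exceed 0.50 (Section 7.1.2) or be at least 50% (simulation).

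In the Part B conclusions of Appendix 10.5, replace the claim about overdose selection in all scenarios with the Scenario 2 figures (35.5% against 51.1%). Replace the insensitivity claim with the target-selection range (23.1% to 70.4%). For Part A, align the wording of Section 7.1.1 and the appendix; no new simulation is needed.

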7.1.3 Part C

The analysis in this trial is descriptive in nature. No statistical model will be used.

7.2 NULL AND ALTERNATIVE HYPOTHESES

The analyses in this trial are descriptive and exploratory. No formal statistical test will be performed.

7.3 PLANNED ANALYSES

No per protocol set will be used in the analysis. However, important protocol violations will be summarised. The TSAP will specify the important protocol violations in detail.

In Parts A and B, for the determination of the MTD, only MTD evaluable patients will be considered. For the analysis of secondary and further endpoints in Parts A and B and for all analyses in Part C, all patients in the treated set (i.e., patients treated with at least one dose of trial medication) will be included in the analysis. Any other analysis sets will be defined in the TSAP.

7.3.1 Primary endpoint analyses

Part A:

- In order to identify the MTD of BI 891065, the number of evaluable patients with DLTs during the MTD evaluation period at each dose level must be presented. Patients who are replaced during the MTD evaluation period will be excluded from the determination of MTD.

For the analysis of tolerability and safety, please refer to Section [7.3.4](#).

Part B:

- In order to identify the MTD of BI 891065 in combination with BI 754091, the number of evaluable patients with DLTs during the MTD evaluation period at each dose level must be presented. Patients who are replaced during the MTD evaluation period will be excluded from the determination of MTD.

For the analysis of tolerability and safety, please refer to Section [7.3.4](#).

Part C:

- The OR by Investigator assessment will be analysed descriptively in terms of objective response rate (ORR), defined as the proportion of patients with best overall response of

CR or PR. The primary analysis of Part C will take place after the last patient was treated for at least 18 weeks.

